11.4 Summary Tables

Summary tables (descriptive statistics and/or frequency tables) will be provided for all variables as appropriate. Continuous variables will be summarized with descriptive statistics (n, mean, standard deviation (SD), median, minimum, and maximum). Frequency count and percentage of subjects or eyes within each category will be provided for categorical data.

11.5 Statistical Analysis

11.5.1 Success Rates – Two Designs versus One Design

Fit acceptance (0=Unacceptable, 1=Acceptable) will be analysed using a generalized linear mixed model with a binary distribution and a logit link function. Lens type will be included as a fixed effect and subject will be included as a random effect.

If the incidence rate is too low or there are problems with the convergence of the above model, the method of Wilson⁵ will be used to evaluate the confidence intervals.

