NO. SITES:	Two sites in UK: Visioncare Research Ltd, Farnham; Aston Research Clinic, Birmingham
END POINTS:	Completion of assessment of three pairs of lenses or discontinuation.
VISITS/SCHEDULE:	One visit
PROCEDURE:	Lenses will be inserted and each pair assessed after ~30 minutes.
CLINICAL VARIABLES:	
Primary variables:
 
Lens fit: horizontal* & vertical* centration (mm), post-blink movement in primary gaze* (mm), version lag (mm), edge tightness (0-4), tightness (push-up %), horizontal corneal overlap (mm)*, diameter acceptance (mm), overall fit acceptability (0-5), fit success rate (%).
 
Corneal topography: Sim-K-readings and corneal shape factor (Medmont), horizontal HVID* (photo slit lamp) corneal sagittal height, corneal diameter (Visante OCT).
 
* From photographs / video

THEORETICAL FIT VARIABLES:	Edge strain (%), corneal overlap (mm), fit success (Yes/No) based on following criteria: Edge strain: 0-6%, Horizontal corneal overlap: 0.2-1.2mm.

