1 INTRODUCTION

Since ocular topographies vary within the population,¹ it is important that contact lens designs are selected that comfortably and successfully fit a wide range of eyes. Multiple designs generally give a wider coverage of the population than single designs. Because soft contact lenses are generally not available in a wide range of parameters, it is difficult to evaluate the effectiveness of design combinations. However, senofilcon A lenses have recently become available in multiple diameters, which offers the opportunity to explore the utility of various design combinations.

Computer modelling provides useful insights into the relationship between lens design and fit and allows an estimation of the fitting success rate for a given lens design on a given population.^{2,3} Recent calculations suggest that a combination of multiple diameter designs is likely to be more successful than multiple base curves of identical lens diameter.⁴

The main purpose of this study is to evaluate the fitting success of various combinations of senofilcon A lens designs. A secondary purpose will be to evaluate the validity of the Young soft contact lens fit model.²

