2 STUDY OBJECTIVES

- i. To compare the lens fitting success rates for three combinations of senofilcon A lens pairs when fitted to a population skewed to larger corneas.
- ii. To compare the actual fitting success rates of senofilcon A lenses with theoretical values from the Young model.²
- iii. To compare the fitting characteristics of senofilcon A lenses (tightness, corneal overlap) with theoretical values from the Young model.

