2.1 Hypotheses

The following hypotheses will be tested:

- i. The fitting success rate for a combination of two senofilcon A designs is greater than for a single design when fitted to a population skewed to larger corneas.
- ii. The fitting success rates for senofilcon A designs are equivalent to those predicted by the Young model.
- iii. The fitting characteristics (tightness, corneal overlap) for senofilcon A designs are equivalent to those predicted by the Young model.

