3.1 Randomisation

Subjects will wear each of the three lens types bilaterally in random succession. A random number generator (Microsoft Excel) will determine the randomisation of lenses to subjects, which is then incorporated into the Randomisation Log.

The randomised assignment of subjects will be performed at the first assessment prior to the first randomised lens fitting. The following must be ensured prior to randomisation:

- Informed consent has been obtained
- Subjects meet all inclusion / exclusion criteria
- Subject history and baseline information have been collected

Subjects who are discontinued may be replaced in order to achieve the targeted minimum number of cohort subjects, but the ID number will not be reused.

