11.5.2 Success Rates – Actual versus Theoretical

Fit acceptance (0=Unacceptable, 1=Acceptable) will be analysed using a generalized linear mixed model with a binary distribution and a logit link function. Lens type, period, and the lens by period interaction will be included as fixed effects and subject will be included as a random effect. The proportion of eyes with acceptable lens fit with each lens type will be calculated with 95% confidence intervals. These confidence intervals will be compared to the theoretical success rates.

If the incidence rate is too low or there are problems with the convergence of the above model, the method of Wilson⁵ will be used to evaluate the confidence intervals.

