11.5.3 Fitting Characteristics – Actual versus Theoretical

The fitting characteristics will be analysed separately for tightness and corneal overlap using linear mixed models. The regression models will include the experimental design factors: lens type, period, and the lens by period interaction as fixed effects, and subject as a random effect. Comparisons will be carried out using 95% confidence intervals constructed of least-square means (LSM) from the linear mixed models.

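### The model stated in 11.5.1 compares single lenses and forms no two-design outcome or contrast, so as written it does not test co-primary hypothesis i

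*Protocol*

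**What the plan says.** The Introduction gives the aim: "The main purpose of this study is to evaluate the fitting success of various combinations of senofilcon A lens designs". Objective i is "To compare the lens fitting success rates for three combinations of senofilcon A lens pairs", in a population skewed to larger corneas. Hypothesis i (section 2.1) reads "The fitting success rate for a combination of two senofilcon A designs is greater than for a single design". Section 11.2 makes it one of three co-primary hypotheses, requires all three to be met, and makes every test two-sided.

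The only analysis given for hypothesis i is section 11.5.1. Its outcome is binary fit acceptance, modelled with a logit link, and "Lens type will be included as a fixed effect and subject will be included as a random effect". If the model fails, Wilson intervals are to be used; no comparison is named there either.

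The meaning of *lens type* comes from other sections. Section 3.1 says "Subjects will wear each of the three lens types bilaterally in random succession". Section 11.5.2 says "The proportion of eyes with acceptable lens fit with each lens type will be calculated with 95% confidence intervals". Section 11.5.3 says "The regression models will include the experimental design factors: lens type, period, and the lens by period interaction as fixed effects". In all three places the term means a single lens as worn. The Synopsis, under Test Products, once counts two lens types, meaning the two brands; that use pools the two base curves of one brand and gives no combination either.

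**The concern.** A lens-type effect shows whether one lens fits acceptably more often than another. Hypothesis i asks whether having two designs available rescues eyes that one design fails. That depends on whether the same eyes fail both lenses, which is a joint property of two results on one eye. A model with one row per lens and lens type as its only fixed effect never forms that joint result.

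Two errors are then possible. A lens-type p-value could be reported as support for hypothesis i when the second design adds nothing over the better lens. Or no lens effect could be found, and hypothesis i judged unmet, although combinations do much better. Because all three co-primaries must be met, the trial's overall conclusion depends on a hypothesis for which no valid test is stated.

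**Working it through.** **1. The plan's own figure.** Section 11.1 states ±5.0% for an 80% interval at 90% success with 60 subjects. Check: 1.2816 × √(0.9 × 0.1 / 60) = 0.0496. It reproduces, but it is the precision of one proportion. Section 11.1 also claims to differentiate 85% from 95% and sizes paired differences in tightness and corneal overlap. None of these is a combination-versus-single comparison.

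**2. Do lens-type effects fix combination rates?** Take 60 subjects, 120 eyes, lenses A, B and C each acceptable on 108 eyes (90%). Assume a combination succeeds on an eye if at least one of its two lenses is acceptable; the protocol gives no rule.

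| Which eyes fail | A, B, C | AB | AC | BC |
|---|---|---|---|---|
| Same 12 for all lenses | 108 each | 108 (90%) | 108 (90%) | 108 (90%) |
| A and B the same 12, C another 12 | 108 each | 108 (90%) | 120 (100%) | 120 (100%) |
| Three separate sets of 12 | 108 each | 120 (100%) | 120 (100%) | 120 (100%) |

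Every lens-type log-odds difference is zero in all three rows.

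**3. The opposite case.** Let A fail on 24 eyes, and B and C on the same 6 of those 24. Acceptable counts are 96, 114 and 114. The B-versus-A log-odds difference is ln(114/6) − ln(96/24) = 2.944 − 1.386 = 1.558. A logit model clustered on subject (GEE, standing in for the mixed model) gives p = 0.003 if both eyes of a subject fail together, and p = 0.00003 if failing eyes are in different subjects. Yet AB is 114 of 120 (95%), the same as B alone. Whether two designs beat one depends here on the comparator, which the plan does not name.

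**4. What criterion could show that hypothesis i is met?** Under the either-lens rule a combination cannot do worse than one of its own lenses, so losses are impossible. Suppose 4 of 60 subjects gain on one eye each.

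- Subject mean differences: four of 0.5 and fifty-six of 0; mean = 2/60 = 0.0333.
- Variance = (4 × 0.25 − 60 × 0.0333²)/59 = 0.0158; standard error = √(0.0158/60) = 0.0162.
- Lower 95% limit = 0.0333 − 2.001 × 0.0162 = +0.0008, just above zero.
- Exact two-sided sign test: 2 × 0.5⁴ = 0.125. Five gains give 0.0625 and six give 0.031.

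The t-interval therefore passes with four gaining subjects, where the exact test needs six. With 40 subjects four also suffice for the t-interval (lower limit +0.0014).

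**5. Chance of passing against a lens inside the combination.** Simulation with all lenses at 90% and assumed latent correlations of 0, 0.5, 0.7 within eye paired with 0, 0.3, 0.5 between eyes. The true gain is then 9.0, 6.8 or 5.3 points.

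| Criterion | 60 subjects | 40 subjects |
|---|---|---|
| t-interval lower limit above zero | 0.83 to 0.99 | 0.55 to 0.92 |
| Exact sign test, at least 6 gaining subjects | about 0.57 to 0.96 | about 0.21 to 0.70 |

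**The case against.** The best defence is that 11.5.1 was meant as a combination analysis. Its heading says so. The sentence about the proportion of eyes for each lens type stands in 11.5.2, not here. The period terms kept in 11.5.2 and 11.5.3 are absent, which suits a derived combination outcome, since that has no single wearing period. Read as single lenses, 11.5.1 nearly duplicates 11.5.2. The derivation, the comparator and the interval method could then be left to a SAP that is not at hand.

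The point about intent stands, and the plan should be read as meaning to compare combinations. But intent supplies neither the outcome nor the factor. The text fixes *lens type*, a term with a settled meaning elsewhere. A SAP that follows it compares single lenses; one that tests hypothesis i must replace both outcome and factor, and so departs from the protocol. This goes beyond detail left open.

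It is also fair that the counts above are constructed and rest on an either-lens rule. They show that single-lens rates leave combination rates open; they do not size an error in this trial. The defect itself does not need that rule, because any combination rule uses the joint result of two lenses on one eye.

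The wording of objective i adds some doubt. *Pair* also means the right and left lenses of one type, as in the Synopsis end point, "Completion of assessment of three pairs of lenses or discontinuation". Read with the Introduction, combinations of two designs is the natural sense.

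**Conclusion.** The point holds for the analysis as written: 11.5.1 states a comparison of single lenses and does not test hypothesis i. Because this is a co-primary hypothesis, it should be corrected before the lens codes are unmasked.

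Three stronger readings are not supported. A reader might infer that the trial cannot test hypothesis i at all. It can, since every subject wears all three lenses on both eyes and the joint results are collected. A reader might infer that section 11.1 sizes only a single proportion. It does more than that; what it lacks is any sizing of a combination against a single design. And a reader might infer that adding a combination outcome and asking for a confidence limit above zero is enough. For a lens inside the combination it is not, because the difference cannot be negative and four gaining subjects would pass.

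The 90% to 100% range rests on the either-lens rule. The pass probabilities rest also on 90% success for every lens and on the assumed correlations.

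**What to change.** In section 11.5.1, for hypothesis i:

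- Replace the per-lens outcome and lens-type factor with a per-eye combination outcome built from the joint results of two designs (for example, at least one acceptable), for 8.40+8.80, 8.40+8.50 and 8.80+8.50.
- Name in advance one combination and one single-design comparator. Estimate the paired difference in success with a 95% interval that accounts for two eyes per subject.
- Where the comparator belongs to the combination, state that the difference cannot be negative under the either-lens rule. Judge the hypothesis met by an exact subject-level paired test (at least six gaining subjects when no losses are possible) or against a minimum gain the sponsor sets beforehand, and not by a t-interval limit above zero. Report the share of eyes gained with its interval.
- In objective i, write *combination* in place of *pair*.

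The cost is one derived variable and some rewording, with no new data. The downside is limited power at the lower end of the planned 40 to 60 subjects, as the last table under the working shows. The plan should state that limit, since the exact test is harder to pass than the t-interval and section 11.1 offers no sizing for this comparison.

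### The hypothesis i model leaves out period, which the other two models include, and no balance of lens orders is stated: a small loss of precision, not a bias

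*Protocol*

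**What the plan says.** Hypothesis i (section 2.1), which is set in eyes with larger corneas, reads in part: "The fitting success rate for a combination of two senofilcon A designs is greater than for a single design when fitted to a population skewed". Its analysis, section 11.5.1, is a logit mixed model for fit acceptance, specified thus: "Lens type will be included as a fixed effect and subject will be included as a random effect". Period does not appear.

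Section 11.5.2 uses the same outcome, distribution, link and random subject for hypothesis ii, but a different fixed part: "Lens type, period, and the lens by period interaction will be included as fixed effects". Section 11.5.3, for tightness and corneal overlap, says in part: "The regression models will include the experimental design factors: lens type, period, and the lens by period interaction as fixed effects, and subject as a". The sentence closes by making subject the random term.

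On the design, section 3.1 states: "Subjects will wear each of the three lens types bilaterally in random succession". On the method it states: "A random number generator (Microsoft Excel) will determine the randomisation of lenses to subjects, which is then incorporated into the Randomisation Log". It mentions neither blocks nor balance over the orders, and it does not call the draw unrestricted.

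Section 5.4 allots 30 enrolment numbers to each of two sites. Section 11.2 makes hypothesis i one of three co-primary hypotheses, all of which must be met.

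**The concern.** The protocol gives one outcome two different fixed-effect structures and does not explain why. This is a choice the protocol itself fixes, not a detail it defers. The model without period serves the comparison that the Introduction calls the main purpose of the study.

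Three pairs are worn one after another in a single visit, and overall fit is an investigator's grade. Drift in grading or adaptation of the eye could therefore shift the success rate from one period to the next. If one lens happens to be worn early more often than another, part of any such shift appears in the lens difference. A period term removes that part from a lens-level comparison, and balanced orders prevent it from arising. Section 11.5.1 has no period term, and section 3.1 promises no balance.

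**Working it through.** **Inputs.** n = 60 and a 90% success rate (section 11.1); 40 to 60 subjects (section 5.1); three periods, six possible orders. The protocol gives no size for a period effect, so total shifts of 5 to 20 points from period 1 to period 3 are assumed. Independent, equally likely orders are also assumed, as the least favourable reading of section 3.1.

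**The plan's own figure.** The 80% half-width is 1.2816 × √(0.9 × 0.1 / 60) = 0.0496, or 4.96 points. The stated ±5.0% reproduces.

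**Chance order component in a two-lens difference.** Each subject contributes the difference between two distinct period effects. Under random order its mean is 0 and its variance is the mean of the three squared period differences. So SD = √(mean squared difference / n).

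| Assumed period effects (points) | Mean squared difference | SD, n = 60 |
|---|---|---|
| 0, 2.5, 5 | (6.25 + 6.25 + 25)/3 = 12.5 | 0.46 |
| 0, 5, 10 | (25 + 25 + 100)/3 = 50 | 0.91 |
| 0, 10, 20 | (100 + 100 + 400)/3 = 200 | 1.83 |

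For the middle row, the 95% range at n = 60 is ±1.96 × 0.913 = ±1.79 points. At n = 40 the SD is √(50/40) = 1.12.

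**Simulation.** 4,000 runs with n = 60, two eyes per subject, random-intercept logit data and no true lens difference. A within-subject linear contrast stands in for the mixed model. Each cell gives the result without / with a period term.

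| Success by period | Orders | SD of lens difference (points) | Two-sided type I error (%) |
|---|---|---|---|
| 90/90/90% | independent | 3.519 / 3.565 | 5.28 / 5.35 |
| 90/86/82% | independent | 4.009 / 3.988 | 5.00 / 4.85 |
| 90/82/72% | independent | 4.780 / 4.528 | 5.45 / 5.43 |
| 90/90/90% | balanced | 3.514 / 3.514 | 5.05 / 4.98 |
| 90/86/82% | balanced | 3.992 / 3.992 | 4.80 / 5.10 |
| 90/82/72% | balanced | 4.419 / 4.419 | 3.65 / 4.90 |

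- Mean estimates lay within 0.2 points of zero, with and without period alike.
- The simulation error on the type I rates is √(0.05 × 0.95 / 4000) = 0.34 percentage points, so no inflation is seen.
- With independent orders, omitting period costs 4.009/3.988 = 1.005 to 4.780/4.528 = 1.056 in SD, that is 0.5 to 5.6%. With no period effect, including it costs 3.565/3.519 = 1.013, or 1.3%.
- With balanced orders the term costs nothing. It also takes the period variation out of the residual; without it the test is conservative under a strong period effect (3.65%).

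**Sample log (Appendix 2).** The 20 template rows count ACB 4, BCA 4, ABC 4, CBA 3, CAB 3, BAC 2. Over periods 1/2/3, lens A falls 8/5/7, B 6/7/7 and C 6/8/6. With period effects 0, 5, 10 the lens averages are A (25 + 70)/20 = 4.75, B (35 + 70)/20 = 5.25 and C (40 + 60)/20 = 5.00. The contrasts shift by −0.50 (A−B), −0.25 (A−C) and +0.25 (B−C) points.

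**The combination contrast.** A combination result draws on two lenses worn in two periods. Over the six orders each lens is in each period twice, so each pair of lenses occupies each pair of periods twice. In a full set of 30 per site that is 10 subjects each.

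**The case against.** The strongest reply has four parts.

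- **The method is not known to be unrestricted.** A reader might infer from the Excel generator that orders are simple random draws. Section 3.1 does not say so: a restricted list can also be made with a generator, and the detail may sit in a randomisation plan that is not shown. This stands. The fair statement is that no balance is stated.
- **The sample log is no evidence of harm.** A reader might take lens A being first in 8 of 20 rows as proof of imbalance. The log is a template of 20 rows, while section 5.4 allots 30 numbers per site. The best possible split of 20 over six orders is 4/4/3/3/3/3, and the log is one subject away from it. Under simple randomisation only about 5.8% of draws are as even or more so. Its first six rows contain ACB twice and CAB not at all, so it is not permuted blocks of six, but it shows nothing harmful. This stands too.
- **The mechanism is thin.** Each pair is new, settles for about 30 to 45 minutes and is discarded, and fit is graded without regard to comfort or vision. Nothing in the protocol points to a 10-point period effect. That is fair, and it is why the effect sizes here are only assumptions. Yet the protocol itself judges period worth modelling in the other two analyses, one of them on this same outcome.
- **A period term does not fit the hypothesis as worded.** A combination has no single period value, and the Wilson fallback in 11.5.1 cannot carry a period term either. This stands, and it limits what the term can do. It strengthens the case for balanced orders, which need no model.

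**Conclusion.** The inconsistency is real and minor. Section 11.5.1 omits a design factor that sections 11.5.2 and 11.5.3 include, no reason is given, and section 3.1 states no balance that would make the omission harmless.

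A reader might infer that order effects bias the lens comparison or inflate its type I error. The design does not support that: randomised order makes the expected contribution zero, and the simulated error rates do not differ with and without period. What is left is a chance shift with an SD of about 0.5 to 2 points in a two-lens difference at n = 60, and about 0 to 6% in SD to be gained. Nor is 11.5.1 the sole primary model; it is one of three co-primary analyses.

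These sizes rest on assumed total period shifts of 5 to 20 points, on independent equally likely orders, and on a linear contrast in place of the logit mixed model. The conclusions of the study are unlikely to turn on this point. It is worth correcting because the correction is nearly free.

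**What to change.** 1. In section 11.5.1, add period as a fixed effect to the lens-level model, in line with 11.5.2 and 11.5.3, or state why it is left out. Only the main effect of period is needed for this purpose.
2. In section 3.1, state that the Randomisation Log is generated in permuted blocks of the six orders within each site. Thirty numbers per site is 30/6 = 5 full sets.
3. Say in 11.5.1 that for the combination-versus-single contrast, and for the Wilson fallback, protection against order effects comes from the balanced orders.

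The cost is one model term and a differently built list; period is already recorded. With balanced orders the term costs no precision; with unbalanced orders and no period effect it costs about 1.3% in SD. If recruitment stops below 60, or subjects drop out of the per-protocol set, balance becomes approximate. The period term then covers the remainder for the lens-level comparison only.

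A separate and larger matter is that lens type as a fixed effect does not by itself define the combination-versus-single contrast. Adding period does not resolve that.
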